## Statistical Analysis Plan

- Disease control – defined as a CR, PR, or SD, according to RECIST version 1.1 criteria, at 12 weeks.
- DOR according to RECIST version 1.1 criteria (measured from the time measurement criteria are first met for CR or PR, whichever is first recorded, until the first date that recurrent or PD is objectively document (taking as reference for PD the smallest measurements recorded on study).).
- PFS – defined as the time from randomization to the first documentation of PD as determined by the Investigator or death from any cause, whichever occurs first.
- OS – defined as the time from randomization to death from any cause.
- Best overall response (including CR, PR, SD, and PD), according to RECIST version 1.1, ordered from best to worst.
- Survival at 12 months (OS-12) –defined as the percentage of patients who have survived at least 12 months from the date of randomization.

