**Table 2. Definition of Analysis Populations**

| Analysis Set    | Definition  |
|------------------------|--|
| All Patients           | All patients who provided written informed consent (i.e., including screen failures)   |
| Full Analysis          | All patients who were either assigned or randomized to study.  |
| Safety                 | All patients who received at least 1 dose of AZD9150, AZD5069, or MEDI4736.  |
| Pharmacokinetics (PK)  | All dosed patients with reportable AZD9150, AZD5069, treme or MEDI4736 plasma concentrations except for important protocol deviation. The important protocol deviations will be determined by the clinical team during the Blind Data Review Meeting (BRDM) planned to take place just prior to the final Database Lock (DBL). |
| Pharmacodynamics (PDN) | All patients who provided biological samples for pharmacodynamic research except for important protocol deviation. The important protocol deviations will be determined by the clinical team during the Blind Data Review Meeting (BRDM) planned to take place just prior to the final Database Lock (DBL).                    |

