## Statistical Analysis Plan

| Analysis Set | Definition  |
|--------------|---|
| Efficacy     | 
All patients with unidimensional measurable disease at baseline as per the RECIST version 1.1 criteria who received at least 1 dose of study treatment (Part A) <del>barring</del> except for important protocol deviation. All patients with unidimensional measurable disease at baseline as per the RECIST version 1.1 criteria who were randomized to study treatment and received at least 1 dose of study treatment (Part B) except for important protocol deviation. Patients who have been manually assigned to treatment in Part B will be excluded from this analysis set.
 
The important protocol deviations will be determined by the clinical team during the Blind Data Review Meeting (BRDM) planned to take place just prior to the final Database Lock (DBL).
 |

While the definitions of several of the various analysis sets apply to both Part A and to Part B of the study, the data for patients from Part A and Part B will be summarized separately.

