**Table 3. Summary of Outcome Populations and Analysis Sets**

| Outcome variable                    | Populations                 |
|--|------------------------------------|
| Efficacy data                       |                                    |
| Disposition                                | All Patients, Full analysis |
| Demography                                 | Safety                      |
| OR*, disease control, DOR*, PFS, OS, OS-12 | Efficacy                    |
| Safety data                         |                                    |
| Relevant Medical History                   | Safety                      |
| Current Medical Condition at Entry         | Safety                      |
| Exposure                                   | Safety                      |
| Adverse events (including SAEs and DLTs)   | Safety                      |
| Laboratory measurements                    | Safety                      |
| Vital signs                                | Safety                      |
| Physical examinations                      | Safety                      |
| ECGs                                       | Safety                      |
| Pharmacokinetic data                | Pharmacokinetic             |
| Pharmacodynamic data                | Pharmacodynamic             |

\* Patients who are evaluable for the analysis of OR and DOR are those with measurable disease at baseline

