## Statistical Analysis Plan

### 8. EFFICACY

The following efficacy endpoints will be summarized and analyzed in dose-escalation Part A and dose-expansion Part B:

- Tumour response according to RECIST criteria version 1.1
- Objective response rate (ORR)
- Best overall response rate (BoR)
- Duration of response (DOR)
- Disease control rate (DCR)
- Progression-free survival (PFS)
- Overall survival (OS)

Additionally, survival at 12 months (OS-12) and changes in tumour size will be summarized in Part B.

For dose-escalation Part A, all efficacy data will be summarized by treatment group using descriptive statistics only.

For dose-expansion Part B, all efficacy data will be summarized by treatment group using descriptive statistics and two-sided 80% confidence intervals (CIs) will be provided for the parameter estimates.

No inferential analyses will be conducted to compare the efficacy between treatment groups in either Part A or Part B.

All efficacy data will be analyzed using the Efficacy Set.

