## Statistical Analysis Plan

### 8.3.9. Survival at 12 Months (OS-12)

Overall survival at 12 months (OS-12) is defined as the percentage of patients surviving at 12 months after randomization to study drug.

Should a patient's vital status at 12 months be unknown, the patient will be considered to be deceased when estimating OS-12. This approach is a conservative one and assumes that patient loss is related to mortality.

An exact two-sided 80% CI for OS-12 will be computed using the Clopper-Pearson method (Clopper and Pearson 1934). Analysis of this secondary endpoint will use the Safety set.

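### Survival at 12 months is assigned to the Safety set in SAP 8.3.9 but to the Efficacy set in Table 3 and Section 8, so one secondary endpoint has two denominators

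*SAP*

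**What the plan says.** Three places in the SAP assign an analysis set to OS-12.

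- **SAP 8.3.9** (Survival at 12 Months): "Analysis of this secondary endpoint will use the Safety set".
- **SAP Section 5, Table 3**, which exists to map each endpoint to its set: the row "OR*, disease control, DOR*, PFS, OS, OS-12" carries the Efficacy population.
- **SAP Section 8**: OS-12 is named among the efficacy summaries ("Additionally, survival at 12 months (OS-12) and changes in tumour size will be summarized in Part B"), and the section then rules that "All efficacy data will be analyzed using the Efficacy Set".

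SAP 4.2.2 also lists OS-12 as a secondary efficacy endpoint for Part B: "Survival at 12 months (OS-12) –defined as the percentage of patients who have survived at least 12 months from the date of randomization".

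The two sets are defined in SAP Table 2. The Safety set is "All patients who received at least 1 dose of AZD9150, AZD5069, or MEDI4736". The Part B Efficacy set is limited to patients with measurable disease at baseline "who were randomized to study treatment and received at least 1 dose of study treatment (Part B) except for important protocol deviation", and the entry adds: "Patients who have been manually assigned to treatment in Part B will be excluded from this analysis set".

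SAP Section 13, on changes from the protocol, mentions no special set for OS-12. Protocol Section 8.10 asks for the 12-month survival proportion with an exact 80% interval, and also for the Kaplan-Meier probability at 12 months, but names no set for either.

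**The concern.** A programmer following 8.3.9 and a programmer following Table 3 would produce different denominators for the same table, and each could cite the SAP. Three things follow.

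1. **A barred patient enters an efficacy endpoint.** Protocol Sections 4.2.2 and 7.7.7 say that one patient was manually placed in Arm B1 and will be left out of any efficacy analysis. SAP 3.4.2 says the same of such patients in general. Under 8.3.9 that patient, once dosed, is counted in OS-12.
2. **Companion estimates describe different patients.** SAP 8.3.8 estimates overall survival in the Efficacy Set. The crude 12-month proportion and the survival curve would then sit in the same report on different populations.
3. **The choice stays open.** The trial is open-label, and the important deviations that shape the Efficacy set are settled just before final database lock. With two printed rules, the set can be picked when outcomes are already visible.

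**Working it through.** **Step 1: the assignments side by side**

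| Place | Set for OS-12 |
|---|---|
| SAP 8.3.9 | Safety |
| SAP Table 3 | Efficacy |
| SAP Section 8, general rule | Efficacy |
| SAP 8.3.8 (overall survival, for comparison) | Efficacy |
| SAP Section 13 | not mentioned |
| Protocol 8.10 | not stated |

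Taking the specific text over the general could reconcile 8.3.9 with Section 8. It cannot reconcile 8.3.9 with Table 3, because Table 3 names OS-12 explicitly.

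**Step 2: who is in one set but not the other (Part B)**

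- Manually assigned patients: one documented, in Arm B1.
- Patients with important protocol deviations: number not given, decided before database lock.
- Patients without measurable disease: should be close to none, because measurable disease is an inclusion criterion for everyone (protocol 3.1.1).

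**Step 3: size, by illustration**

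The documents state no expected OS-12 rate and no count for either set, so there is no planned figure to reproduce. The numbers of survivors and of extra patients below are assumptions. The estimate is x/n with the exact two-sided 80% Clopper-Pearson interval that 8.3.9 specifies: lower limit is the 0.10 quantile of Beta(x, n − x + 1), upper limit is the 0.90 quantile of Beta(x + 1, n − x).

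*Efficacy set of 12 (the planned size of Arms B5 and B6), 5 alive, one further patient in the Safety set:*

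- 5/12 = 41.7% (21.9% to 63.8%)
- further patient dead or of unknown status: 5/13 = 38.5%
- further patient alive: 6/13 = 46.2%

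*Efficacy set of 48, 24 alive, three further patients who died:*

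- 24/48 = 50.0% (39.9% to 60.1%)
- 24/51 = 47.1% (37.4% to 56.9%)

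*Taking the Safety set as the fixed starting point and removing k patients.* Each range runs from all k alive to all k dead or of unknown status:

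| Safety set | k | Efficacy-set OS-12 |
|---|---|---|
| 10/20 = 50.0% | 1 | 9/19 = 47.4% to 10/19 = 52.6% |
| 10/20 = 50.0% | 3 | 7/17 = 41.2% to 10/17 = 58.8% |
| 24/48 = 50.0% | 1 | 23/47 = 48.9% to 24/47 = 51.1% |
| 24/48 = 50.0% | 3 | 21/45 = 46.7% to 24/45 = 53.3% |
| 24/48 = 50.0% | 5 | 19/43 = 44.2% to 24/43 = 55.8% |

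So one patient is worth about 2.6 points at 20 patients and about 1 point at 48.

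**The case against.** The strongest reply accepts the contradiction but disputes its weight and the choice of set.

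- **All treated patients is a reasonable denominator for survival.** Measurable disease matters for response, not for knowing whether a patient is alive, and the protocol names no set. This stands as an argument about design. However, a sponsor who wanted it would have to write an exception into Section 8 and correct Table 3, and neither was done.
- **The Efficacy definition requires randomization, and Arms B7 and B8 are not randomized.** Read literally, moving OS-12 to the Efficacy set would empty both arms. The wording is a real fault, but it hits every Part B efficacy endpoint, including the primary one. It needs its own correction and gives no reason to treat OS-12 alone differently.
- **The Efficacy set carries its own discretion**, through deviations judged just before lock. True, but that discretion already applies to overall survival and response.
- **Aligning the sets does not make the two 12-month figures identical.** SAP 8.3.9 counts unknown status as death, while 8.3.8 censors it and also censors monotherapy patients at the switch to combination. This stands: the fix removes the population difference, not these differences in handling.
- **The effect is probably small.** Only one affected patient is documented, Part B efficacy is descriptive, and OS-12 drives no stopping rule. This also stands and limits the impact.

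**Conclusion.** The concern holds. The SAP gives OS-12 two analysis sets that differ by definition, and no text in either document chooses between them. Followed as written, 8.3.9 puts at least one patient whom both documents exclude from efficacy analyses into a named secondary efficacy endpoint, provided that patient was dosed.

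The numerical effect cannot be derived from the documents. Under the assumptions shown it is about 1 point per patient in a 48-patient arm and 3 to 5 points in a 12-patient arm, which is small against the width of the 80% interval. The primary endpoint is not touched. The correction should be made because the error is certain, the cost is negligible, and leaving it allows a choice after the data are known.

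**What to change.** In the last sentence of SAP 8.3.9, replace Safety set with Efficacy set. This agrees with Table 3, Section 8, the overall survival analysis in 8.3.8 and the exclusion of manually assigned patients. The cost is one word in the SAP, with no new data and no change to sample size.

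If the sponsor does intend all treated patients for this endpoint, the alternative is to state the exception in Section 8, correct the Table 3 row, and explain why the manually assigned patient counts. Either way, one set should be fixed before database lock.

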### 8.3.10. Time to First Response

Time to first response is defined as the time (days) from the date of treatment allocation (Part A) or randomization to study drug (Part B) to the date of confirmed CR or PR. This definition will apply regardless of whether the patient withdraws from treatment or receives another anti-cancer therapy prior to response.

The time to first response will be derived based using scan/assessment dates and not visit dates. PFS times will be derived using assessment dates from the "Tumour Assessment" CRF pages.

RECIST assessments/scans contributing towards a particular visit may be performed on different dates. The following rules will be applied:

- Date of response will be determined based on the **earliest** of the dates of the component that triggered progression
- When censoring a patient for time to first response, the patient will be censored at the study day of last evaluable assessment for subjects without response

Time to first response will be analyzed for all evaluable patients using a K-M survival analysis. The number of events, percentiles for the time to first response (25%, 50% (median), and 75% percentiles), and the proportion of patients who responded at 1, 2, 3, and 4 months will be summarized by treatment group. For Part B only, two-sided 80% CIs will be provided for the median PFS times (Brookmeyer and Crowley, 1982), which can be reported using SAS LIFETEST Procedure with CONFTYPE=LINEAR. The 80% CIs for median PFS is the set of all  $t$  which meets  $|ES(t)-0.5|/se(ES(t)) \leq z_{0.9}$ , where  $ES(t)$  is the estimated survival function and  $se(ES(t))$  is the standard error of  $ES(t)$ . Exploratory Analyses

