## Statistical Analysis Plan

response will be used, not the confirmatory scan date. If there are more than one RECIST assessment which contributes to a particular visit, e.g. two different body areas, the later of the two would be used to declare CR/PR.

Best overall response (BOR) will be determined programmatically based on RECIST using all site investigator data up until the first progression event. The denominator will be consistent with that used in the ORR analysis.

For patients whose progression event is death, BOR will be calculated based upon all evaluable RECIST assessments prior to death.

For patients who die with no evaluable RECIST assessments, if the death occurs  $\leq 18$  weeks (i.e., 16 weeks + 2 week to allow for a late assessment within the assessment window) after first dose/administration of study medication, then BOR will be assigned to the progression (PD) category. For patients who die with no evaluable RECIST assessments, if the death occurs  $> 18$  weeks after start of treatment then the patient will be counted as a non-responder and BOR will be assigned to the NE category.

A patient will be classified as a responder if the RECIST criteria for a confirmed CR or PR are satisfied at any time following first dose/administration of study medication, prior to RECIST progression and prior to starting any subsequent cancer therapy.

The number and percentage of patients in each of the overall response categories will be reported by treatment group using the Efficacy Set. The best overall response will be listed for each patient.

For Part A, only descriptive summaries of the best overall response will be provided. For Part B, exact 2-sided 80% CIs will be computed for each response level using the method of Clopper-Pearson (Clopper and Pearson 1934).

The Independent Central Review (ICR) adjudicated results of imaging data will be obtained from Paraxel. The data will be used in the standardization of radiological exams from the Investigator Sites for this trial. The objective will be to assess the concordance rate of BOR at both the sample and patient level for the following:

- Best Independent Central Review (BICR) response results compared to programmatically derived BOR
- BICR response results compared to the investigator assessment of BOR, and
- Investigator assessment of BOR compared to programmatically derived BOR.

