### 8.3.3. Duration of Overall Response (DOR)

The duration of response (DOR) is defined as the time from the date of first documented response (CR or PR) until the date of documented progression or death in the absence of disease progression. The time of the initial response will be defined as the latest of the dates contributing towards the first visit response of CR or PR. The end of response should coincide with the date of progression or death from any cause used for the progression-free survival (PFS) endpoint. If progression or death due to any cause does not occur after a response, the patient's DOR will be censored at the date of last tumour assessment (i.e., the PFS censoring time). Only patients who have a CR or PR during the study will be included in the analysis.

The DOR in weeks will be calculated for all patients that experience documented CR or PR during the study in weeks as follows:

$$\text{Duration of response (weeks)} = ((\text{Date of Progression/Death/Censoring} - \text{Date of First recorded CR or PR}) + 1)/7.$$

If there are sufficient data, DOR will be analyzed for all evaluable patients achieving response during the study using a Kaplan-Meier (K-M) survival analysis. Only patients who have a confirmed response will be included in this summary table. A K-M curve will present the distribution of DOR time by treatment group, along with the median DOR, provided it has been reached by the time of analysis. In Part B only, two-sided 80% CIs will be provided for the median DORs (Brookmeyer and Crowley 1982). Swimmer plots that clearly show the profile of each patient who responds will be produced.

In Part B, the Expected Duration of Response (EDOR) will be calculated for each treatment arm by multiplying the proportion of patients responding to treatment and the mean DOR amongst responding patients. Two-sided 80% CIs will also be provided for the EDORs (Ellis et al 2008).

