### 8.3.7. Progression-free Survival (PFS)

Progression-free survival (PFS) is defined as the time (days) from the date of treatment allocation (Part A) or randomization to study drug (Part B) to the date of objective disease progression or death due to any cause, whichever occurs first. This definition will apply regardless of whether the patient withdraws from treatment or receives another anti-cancer therapy prior to progression.

The PFS time will be derived based using scan/assessment dates and not visit dates. PFS times will be derived using assessment dates from the “Tumour Assessment” CRF pages or, if needed, the date of death from the “Death” CRF page.

RECIST assessments/scans contributing towards a particular visit may be performed on different dates. The following rules will be applied:

- Date of progression will be determined based on the **earliest** of the dates of the component that triggered progression
- When censoring a patient for PFS, the patient will be censored at the **latest** of the dates contributing to a particular overall visit assessment

Patients who have not progressed or died at the time of the analysis will be censored at the time of the latest date of assessment from their last evaluable RECIST assessment.

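### SAP 8.3.10 dates first response by the PFS progression rule, takes the earliest scan where the rest of the plan takes the latest, and names median PFS in its confidence interval

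*SAP*

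**What the plan says.** SAP 8.3.10 defines time to first response in days, from treatment allocation (Part A) or randomisation (Part B) to the date of confirmed CR or PR. It then gives these rules:

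- **Date rule:** "Date of response will be determined based on the" earliest "of the dates of the component that triggered progression".
- **Censoring rule:** patients without a response are censored at their last evaluable assessment.
- **Source of dates:** a sentence on the Tumour Assessment CRF pages says that PFS times are derived from them.
- **Interval (Part B):** "two-sided 80% CIs will be provided for the median PFS times", by the Brookmeyer-Crowley method. The next sentence writes out the formula, again for median PFS.

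Other places date the same response differently:

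- **SAP 8.3.3 (DOR):** "The time of the initial response will be defined as the latest of the dates contributing towards the first visit response of CR or PR". Protocol 8.9 has the same rule for DOR.
- **SAP 8.3.2 (BOR):** when more than one assessment contributes to a visit, "the later of the two would be used to declare CR/PR". The same section says that the initial scan showing the response is used, not the confirmatory one.

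The PFS rule in SAP 8.3.7 begins "Date of progression will be determined based on the" and continues with the same earliest-component wording as 8.3.10.

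**The concern.** A rule that dates a response by what triggered progression cannot do its job. SAP 8.2.2 counts a response only if it comes before any evidence of progression, so at the response visit no component has triggered progression.

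The obvious correction, reading response for progression, leaves a second problem. Time to first response would end at the earliest scan of the visit, while DOR for the same patient starts at the latest scan of that visit. One event would have two dates in one report, and the days between them would belong to neither endpoint.

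The interval has a related fault. A programmer who follows the text would produce an interval for median PFS, which 8.3.7 already requires, and none for the median that 8.3.10 reports.

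At stake is whether the reported response times can be reproduced from the SAP. In an open-label study it is better to settle such choices in the SAP than while programming.

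**Working it through.** **1. The interval formula.** The only number stated in 8.3.10 that can be checked is the critical value z_0.9 for a two-sided 80% interval. z_0.9 = 1.2816, and 2 × 0.90 − 1 = 0.80. The level is right, and the condition |ES(t) − 0.5| / se(ES(t)) ≤ z_0.9 is valid for the median of any Kaplan-Meier curve. Only the endpoint named is wrong.

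**2. The date rule read literally.** SAP 8.1 schedules scans on Day 15 of Cycle 2 and then at the start of each later even-numbered cycle. With 28-day cycles, the nominal days are:

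- Cycle 2 Day 15: 28 + 15 = Day 43
- Cycle 4 Day 1: 3 × 28 + 1 = Day 85
- Cycle 6 Day 1: 5 × 28 + 1 = Day 141
- Cycle 8 Day 1: 7 × 28 + 1 = Day 197

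Take a patient whose response is first seen on Day 43. If progression is found on Day 141, the literal rule dates the response 141 − 43 = 98 days late. If it is found on Day 197, the error is 197 − 43 = 154 days. A responder who has not progressed gets no event date, and the censoring rule does not help because it covers only patients without a response.

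**3. The date rule with response substituted for progression.** The rules for one and the same response are then:

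| Place | Date taken |
|---|---|
| SAP 8.3.10 (time to first response) | earliest |
| SAP 8.3.2 (BOR) | later of the two |
| SAP 8.3.3 (DOR) | latest |
| Protocol 8.9 (DOR) | latest |

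The gap is the spread of scan dates within one visit. The documents give no data on that spread, so only an upper bound can be stated, on the assumption that the component scans fall at opposite ends of the visit window. The two documents state different windows, so both are shown:

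- SAP 6.2 and 8.1, ±3 days: 2 × 3 = 6 days
- Protocol 5.3.1 and Table 5, ±7 days: 2 × 7 = 14 days

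For scale, assume that randomisation falls on the first lead-in day. The first scan is then 7 + 42 = 49 days later (7 lead-in days, then 42 days from Day 1 of Cycle 1 to Day 15 of Cycle 2). The bounds are 6/49 = 12% and 14/49 = 29% of that time. The earliest-date rule always gives the shorter time.

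**4. Where the endpoint is used.** Time to first response is absent from the protocol objectives, SAP 4.2.1 and 4.2.2, SAP Table 3 and the list that opens SAP Section 8. SAP Section 8 rules out inferential comparison between groups. The predictive-probability and interim rules count responses and do not use their timing.

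**The case against.** The best defence is that this is a visible carry-over from 8.3.7. The sentence has the date of response as its subject, the neighbouring censoring bullet was adapted correctly, and the interval sentence closes a paragraph about time to first response. SAP 8.3 also promises 80% intervals for all Part B efficacy estimates. A competent programmer would read response for progression and apply the interval to the right curve.

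Most of this stands for the interval: the method is right and the label is wrong. It does not settle the date. Nothing in 8.3.10 tells the programmer to replace *earliest* by *latest*, and that is a real conflict with three other places.

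A reader might infer four stronger things, which the documents do not support:

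- **That the interval itself is invalid.** The formula and level hold for any Kaplan-Meier median.
- **That response times shift by at least 28 days because the confirmatory scan is used.** The phrase about confirmed CR or PR leaves this open within 8.3.10, but 8.3.2 uses the initial scan, 8.3.3 starts from the initial response, and the section title says first response. This is a residual ambiguity to close, not an established shift.
- **That time to response plus DOR must equal PFS.** No section requires it. DOR is in weeks with one day added, and the other two are in days with no stated day count.
- **That the primary result is at risk.** ORR has its own rule in 8.2.2, and BOR, DOR and PFS have theirs in 8.3.2, 8.3.3 and 8.3.7.

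**Conclusion.** The date rule in SAP 8.3.10 is wrong as written, and no other section corrects it. Taken literally, it gives a responder the progression date (98 or 154 days late in the two examples, on nominal scan days) or no date. With the obvious substitution it still differs from the plan's other response dates by up to 6 days under the SAP window or 14 days under the protocol window (12% to 29% of 49 days). Those are upper bounds, resting on scans at opposite ends of the window and randomisation on the first lead-in day; for a patient whose scans all fall on one day the gap is zero. The interval is mislabelled, not miscalculated, but as written 8.3.10 specifies none for median time to first response. The consequence is confined to one descriptive endpoint.

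**What to change.** Edit four sentences in SAP 8.3.10:

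1. **Date rule:** the date of first response is the latest date contributing to the first visit with CR or PR that is later confirmed. Say explicitly that this is the initial scan and not the confirmatory one. This matches SAP 8.3.2, SAP 8.3.3 and protocol 8.9.
2. **CRF-derivation sentence:** replace PFS by time to first response.
3. **Both interval sentences:** replace median PFS by median time to first response, and leave the method and z_0.9 as they are.

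The cost is a short text change and the matching programming specification. No new data are needed, and no other endpoint's rule changes.

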## Statistical Analysis Plan

Data obtained up until progression, or the last evaluable assessment in the absence of progression, will be included in the assessment of ORR. Patients who discontinue study treatment without progression, receive a subsequent anti-cancer therapy (note that for this analysis radiotherapy is not considered a subsequent anti-cancer therapy) and then respond will not be included as responders in the ORR. ORR and the corresponding exact 2-sided 80% confidence interval (CI), calculated using the Clopper-Pearson method (Clopper and Pearson 1934), will be summarized by treatment group. The listing summarizing tumour responses by visit (see Section 8.1) will also indicate whether the patient was a responder.

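### Time to first response: Kaplan-Meier with progressed and dead non-responders censored overstates the later response proportions and distorts the percentiles; the primary ORR is not affected

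*SAP*

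**What the plan says.** SAP 8.3.10 sets the estimator: "Time to first response will be analyzed for all evaluable patients using a K-M survival analysis". For patients who never respond, "the patient will be censored at the study day of last evaluable assessment for subjects without response". Progression and death are not named; they fall under this rule because such patients are without response. The planned outputs are the number of events, the quartiles, and "the proportion of patients who responded at 1, 2, 3, and 4 months will be summarized by treatment group". No competing-event method appears in this section or elsewhere in the SAP.

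Three other rules in 8.3.10 differ from neighbouring sections.

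- **Subsequent therapy.** 8.3.10: "This definition will apply regardless of whether the patient withdraws from treatment or receives another anti-cancer therapy prior to response". Section 8.2.2 says that patients who stop without progression, take another anticancer therapy and "then respond will not be included as responders in the ORR"; radiotherapy does not count as such a therapy there. Section 8.3.2 also requires response before any subsequent cancer therapy.
- **Component date.** 8.3.10: "Date of response will be determined based on the" earliest date of the component behind progression, which has no meaning for a response. Section 8.3.3: "The time of the initial response will be defined as the latest of the dates contributing towards the first visit response".
- **Event date.** 8.3.10 runs the clock "to the date of confirmed CR or PR", which does not settle whether the initial or the confirmatory scan is meant. Section 8.3.2 uses the initial scan.

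The section also speaks of deriving PFS times and of confidence intervals for median PFS, so rules from 8.3.7 appear to have been carried over unadapted.

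**The concern.** Sections 8.2.2 and 8.3.2 count a response only if it precedes progression. By the SAP's own definition, a patient who has progressed or died without responding can no longer become a responder. Censoring that patient tells the Kaplan-Meier method the opposite: that the patient would go on to respond at the same rate as those still at risk. The result estimates response in a hypothetical setting without progression or death. The SAP, however, labels it as a proportion of patients who responded.

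At stake are the later landmark proportions and the quartiles for each arm. They would look more favourable than the data, and a median could be reported in an arm where far fewer than half the patients respond.

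**Working it through.** The SAP states no figure for this endpoint, so there is none to reproduce.

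**Direction.** Kaplan-Meier gives each responder a weight S/n: the current estimate of the proportion without response, divided by the number at risk. At the start this is 1/N. Responses leave it unchanged, since S(1 − d/n)/(n − d) = S/n. Censoring lowers n but not S, so the weight rises. Every response after a censoring therefore counts for more than 1/N. Hence 1 − KM is never below responders/N, and the two are equal only if nobody is censored before the last response.

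**Inputs from the documents.** Arm size 48 (B7, B8) and a 25% response rate, one of the planning values (SAP 3.6.2). Scans at Cycle 2 Day 15, then Day 1 of each later even-numbered cycle (SAP 8.1): days 43, 85 and 141 from Cycle 1 Day 1. Counted from randomization, assumed at about Day -7, these are about 49, 91, 147, 203 and 259 elapsed days.

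**Assumed, not in the documents.** The timing of responses and of the last scan in non-responders. Events are taken before censorings at ties.

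*Example 1.* Responses 7/3/2 at scans 1 to 3; non-responders' last scans 18/8/10.

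| Scan | At risk | 1 − KM | Responders/48 |
|---|---|---|---|
| 1 | 48 | 1 − 41/48 = 14.6% | 7/48 = 14.6% |
| 2 | 48 − 7 − 18 = 23 | 1 − 41/48 × 20/23 = 25.7% | 10/48 = 20.8% |
| 3 | 23 − 3 − 8 = 12 | 1 − 41/48 × 20/23 × 10/12 = 38.1% | 12/48 = 25.0% |

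*Example 2.* Responses 7/3/1/1 at scans 1 to 4; four non-responders with no post-baseline scan, the rest last scanned 16/8/5/2/1 at scans 1 to 5.

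| Scan | At risk | 1 − KM | Responders/48 |
|---|---|---|---|
| 1 | 44 | 1 − 37/44 = 15.9% | 14.6% |
| 2 | 21 | 1 − 37/44 × 18/21 = 27.9% | 20.8% |
| 3 | 10 | previous S × 9/10: 35.1% | 11/48 = 22.9% |
| 4 | 4 | previous S × 3/4: 51.3% | 25.0% |

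**Reading at the planned outputs.**

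- 1 month: before the first scan, so normally zero either way.
- 2 months: after scan 1 only. Gap 0 in Example 1 and 1.3 points in Example 2, from the four unscanned patients.
- 3 months: scan 2 falls at about 91 elapsed days from randomization, which is the SAP's own 3-month length (8.3.4). Whether it is counted depends on the scan window.
- 4 months (about 122 days): after scan 2. Gap 25.7 − 20.8 = 4.9 points and 27.9 − 20.8 = 7.1 points.
- Percentiles: in Example 1, 25% responding is reached at scan 2 instead of scan 3, and no median is reached by either method. In Example 2 a median appears at about day 203, although the true cumulative proportion never exceeds 25%.

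**Sensitivity.** I took responses spread 60/25/10/5% or 40/30/20/10% over scans 1 to 4, response rates of 15 to 35%, and 0 to 20% of non-responders unscanned. The expected 4-month gap then runs from 3.2 points (16.0% against 12.8%) to 11.0 points (40.7% against 29.7%). If all responses fall at scan 1 and everyone is scanned, the gap is zero.

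In 5,000 simulated trials per scenario (n = 48, true rate 25%, 10% of non-responders unscanned), a Kaplan-Meier median was reached in 36 to 63% of trials. Under 0.1% of those trials had an observed response rate of 50% or more.

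**Event date.** All of the above uses the initial scan. If Example 2 is dated at the next scan instead, 1 − KM at scan 2 is 7/28 = 25.0% against 7/48 = 14.6%. The final value is 76.9% for the same 25% ORR.

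**The case against.** The strongest reply is that little of this reaches a planned output. Section 8.3.10 specifies no Kaplan-Meier plot and no proportion beyond 4 months, so end-of-curve values such as 38.1% or 51.3% would not be tabulated; they act only through the percentiles. The 1-month value is unaffected and the 2-month value nearly so. The endpoint appears in neither the SAP 4.2 lists nor the protocol's secondary outcome measures. It enters no stopping rule or interim variable, and no between-group inference is planned. All of that stands, and it limits the point to the later landmarks and the quartiles.

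It also stands that the size rests on assumed timings. The direction does not.

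A reader might infer that the table will openly contradict the primary ORR. The documents do not support that: a 4-month proportion and an ever-responding proportion are different quantities, and in Example 1 they are 25.7% and 25.0%. A reader might also infer that the bias is worst wherever many patients progress early. That does not hold in general, because early censoring inflates the estimate only if responses follow it.

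Counting responses after another therapy could be a deliberate choice. The SAP gives no reason for it, and it leaves two responder definitions in one report.

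**Conclusion.** The point holds in limited form. Censoring non-responders who progress or die makes 1 − KM an upward-biased estimate of the proportion responding whenever later responses occur. With initial-response dating and a 25% response rate, the 4-month excess is about 5 to 7 points in the two examples, and 3 to 11 points over the wider set of staggered timings. The 3-month value may be affected, and the percentiles can be seriously misleading, including a spurious median. These sizes depend on timings that the documents do not give, and the bias vanishes if every patient is scanned and all responses come at the first scan.

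The mismatches on subsequent therapy and response date stand on the text alone. It would be wrong to infer that the primary analysis is compromised: ORR in 8.2.2 is a crude proportion of the Efficacy set with its own exact interval, and nothing in 8.3.10 feeds into it.

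**What to change.** Amend SAP 8.3.10 as follows.

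1. Replace the Kaplan-Meier estimate with the cumulative incidence of confirmed response, with progression and death without response as competing events. Keeping these patients in the risk set to the data cut-off is an acceptable alternative.
2. Give the median time to response among responders only, labelled as such.
3. Use the responder definition of 8.2.2, including its subsequent-therapy rule and its radiotherapy exception.
4. Date the event at the initial response as in 8.3.3 (latest contributing date), and say explicitly that the confirmatory scan date is not used.
5. Remove the PFS wording on dates, derivation and confidence intervals, and state the interval method for the new estimate.

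The cost is SAP wording, one replaced table and its program. No new data are needed.
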